16.2.6. Pharmacokinetics

In stage 1, the pharmacokinetics of RDV will be evaluated using an intensive PK schedule for a small proportion of the subjects enrolled in healthcare institutions to establish the PK model and by population approach (sparse sampling) for the others. Twenty-five evaluable intensive PK evaluations will provide sufficient precision in the estimates of the PK parameters to use as initial estimates in the population model.

The population PK model (stage 1 and stage 2) built using these parameters allows, with a small number of samples per subject, collected at variable times between drug intake and sampling, to reestimate the pharmacokinetic parameters of the drugs as well as their variability in the population. This approach enables to explain the observed variability with various pertinent covariates such as possible antiretroviral co-treatment and patient's characteristics (e.g., BMI, sex, etc.).

Individual pharmacokinetic parameters are derived using Bayesian estimation from the population model. Association between individual exposures (i.e. trough concentration, area under the curve) and efficacy/tolerance endpoints are then investigated. The pharmaco-statistical analysis is performed using non-linear mixed effects modelling software (e.g. Monolix v4.2 or NONMEM v7.3) to calculate the pharmacokinetic parameters of all drugs as well as the covariates associated with inter-subject variability.

Given the reported drug-drug interactions between antiretrovirals and DAAs, RDV, NNRTI or PI morning troughs or mid dose concentrations are systematically measured in HIV/HCV co-infected subjects to verify that RDV as well as antiretrovirals are within exposure targets. Given the metabolic route of elimination of RDV, it is anticipated that drug-drug interactions, if any would be minimal.

Hair analysis has proved to be a suitable method to detect chronic or acute abuse of many drugs of abuse such as opiates, cocaine, amphetamines and many others. Hair samples are collected at baseline and at end of treatment for all subjects where possible. These samples will be used to assess drug use in subjects who fail to meet the primary study endpoint (SVR12).

Data management programs and all statistical analyses except pharmacokinetic modelling will be performed using Stata version 13 or higher.

17. Data Safety Monitoring Board

A Data Safety Monitoring Board (DSMB), composed of diverse members independent of the investigator and sponsors, will be set up prior to study initiation. The DSMB monitors the study in order to ensure that harm is minimized and benefits maximized for the study subjects. They will review the study data at pre-determined intervals and issue recommendations about the study. In particular, they will review the analysis results after each stage of the study. The analysis strategy

will be agreed prior to analysis of the study results and documented in the DSMB Charter. A Charter will define the membership and responsibilities of the DSMB.

18. Adjudications Committees

18.1. Clinical Adjudication Committee

The primary purpose of the Clinical Adjudication Committee is to adjudicate key data to be used for the analysis of the study. A Charter will define the membership and responsibilities of the Adjudication Committee.

18.2. Virology Adjudication Committee

The primary purpose of the Virology Adjudication Committee is to adjudicate key data to be used for the analysis of the study. A Charter will define the membership and responsibilities of the Adjudication Committee.

19. Quality assurance and quality control procedures

19.1. Essential documents

The investigator must maintain adequate and accurate records to enable the conduct of the study to be fully documented and the study data to be subsequently verified. These documents include Investigator's Site File, subject clinical source documents and screening / enrolment logs. The Investigator's Site File will contain the protocol/protocol amendments, CRF and query forms, any forms or documents sent to DNDi Pharmacovigilance (PV), IEC and regulatory approval with correspondence, sample informed consent, drug accountability records, staff curriculum vitae and authorization forms and other appropriate documents/correspondence etc.

19.1.1. Subject identification list/Enrolment log

A subject identification list will be maintained by the sites and will allow reconciliation of subject number and real subject identification in case a follow-up is required. The site keeps this confidential list in the study documents locked cabinet. The subject enrolment log is maintained by the site to document chronological enrolment of subject by study number.

19.1.2. Site signature/authorization log

A site signature list and authorization log will be maintained by the site and completed by each member of the study site to allow identification of the team. On this form, the site principal investigator delegates study activity to the team under his responsibility and updates the form every time a team member is leaving or a new team member is joining.

19.1.3. Curriculum Vitae

Curriculum vitae of each site member will be filed in the investigator file to document qualifications and eligibility to conduct study and /or provide medical supervision of subjects. The curriculum vitae must contain qualifications and training and will be updated when a new information is available. It must be dated and signed.

19.2. Case report forms (CRFs)

Data will be collected by the study personnel authorized by the investigator. It will be supervised by the investigator and signed by the investigator or by an authorized staff member. Study-specific information will be entered into the Case Report Form (CRF). All data will be supported by source data and no data will be entered directly into the CRF. All CRF data will be identified by study subject number only.

The investigator at each trial site should ensure the accuracy, completeness, legibility, and timelines of all data reported to the sponsor in the CRFs and any other additional information that is required.

The investigator is responsible for keeping all consent forms, screening forms, CRF and the completed subject identification code list in a secure location.

After the CRF has been completed, CRFs will be uploaded and data will be entered onto a database using double independent data entry. The trial data will be stored in a computer database maintaining confidentiality in accordance with national data legislation. Source documentation will be monitored by CRAs on a regular basis.

19.3. Record Retention

The investigator must keep all records pertaining to the conduct of the clinical study, ICFs, drug accountability records, source documents, and other study documentation on file for at least 15 years after completion or discontinuation of the study. After that period of time the documents may be destroyed with prior permission from DNDi, subject to local regulations.

Should the investigator wish to assign the study records to another party or move them to another location, DNDi must be notified in advance.

The Investigator must notify the Sponsor in the event of accidental loss or destruction of any study records. If the Investigator leaves the institution where the study was conducted, the Sponsor must be contacted to arrange alternative record storage options. Whenever possible, an original recording of an observation must be retained as the source document. However, a photocopy of a record is acceptable provided it is legible and is a verified copy of the original document. All CRF data entered by the site (including audit trail), as well as computer hardware and software (for accessing the data), will be maintained or made available at the site in compliance with applicable record retention regulations. The Sponsor will retain the original CRF data and audit trail.

19.4. Audits and Inspections

The trial site may also be subject to quality assurance audits by DNDi or designated representatives and/or to inspection by regulatory authorities or Independent Ethics Committees (IEC) to ensure that Good Clinical Practices (GCP) and all aspects of the protocol are followed.

It is important that the investigators and their relevant personnel are available for possible audits or inspections.

The investigators will permit representatives of DNDi and/or of regulatory authorities/IECs direct access to source and trial documents and will allow the review of all CRFs, medical records, laboratory work sheets and assessment of the status of drug storage, dispensing and retrieval at anytime during the study. The corresponding source documents for each subject will be made available provided that subject confidentiality is maintained in accord with local regulations.

19.5. Study Administration

19.5.1. Study initiation

The study will be conducted in accordance to local regulatory requirement. A study may not be initiated until all regulatory requirements are met

The following documents must be obtained or in place prior to the initiation of the study at each site:

- Documentation of IEC approval of the study protocol, informed consent form, case report form, questionnaire and other relevant study related documents.
- Current IEC membership list
- A copy of the protocol signature page signed by the PI
- CTIL approval from the regulatory
- Clinical trial insurance policy
- Clinical Trial Agreement

19.5.2. Notification of primary care physician

The investigator should inform the subject's primary care physician about the subject's participation in the study if the subject has a primary care physician and the subjects agrees to the primary care physician being informed.

19.5.3. Source documents

Qualified representatives of the Sponsor or Sponsor designee will monitor the study. Monitoring visits provide the Sponsor with the opportunity to:

- 1. Evaluate the progress of the study.
- 2. Verify the accuracy and completeness of CRFs and forms/documents sent to DNDi PV.
- 3. Assure that all protocol requirements, applicable laws and/or regulations, and Investigator's obligations are being fulfilled.
- 4. Resolve any inconsistencies in the study records.

Four visit types are planned: pre-study, study start, during the study, and study end. Visits may also be performed by regulatory authorities.

The Investigator must allow the Study Monitor to periodically review, at mutually convenient times during the study and after the study has been completed, all CRFs and office, hospital, and laboratory records supporting the participation of each subject in the study.

The CRFs forms as well as the documents sent to DNDi PV and other documentation supporting the study must be kept up-to-date by the Investigator and the research staff at the investigative site. These study materials must be available for review by the Study Monitor, and/or other qualified representatives of the Sponsor, at each monitoring visit. The study monitor will review the various records of the study (CRFs, subject medical and laboratory records, and other pertinent data including forms/documents sent to DNDi PV). The Study Monitor will verify the CRF data against original source documentation for accuracy and completeness.

The study monitor will identify data discrepancies and collaborate with the Investigator and research staff to resolve the discrepancies in a timely manner. Protocol deviations will also be identified and recorded on a "Protocol Deviation Log" (see section 19.5.6). The study monitor will follow an "Issue Escalation" plan in order to ensure that each issue identified during a monitoring visit is appropriately documented, reported, and resolved in a timely manner in accordance with the plan's requirements.

Monitoring visits to the trial site will be made periodically by DNDi representatives or designated clinical monitors to ensure that GCPs and all aspects of the protocol are followed. Source documents will be reviewed for verification of consistency with data on CRFs. The investigator will ensure direct access to source documents by DNDi or designated representatives.

The investigators will permit representatives of DNDi and/or designated clinical monitors to inspect all CRFs, medical records, and laboratory work sheets, and to assess the status of drug storage, dispensing, and retrieval at any time during the study. The corresponding source documents for each subject will be made available provided that subject confidentiality is maintained in accord with local regulations. The inspections are for the purpose of verifying the adherence to the protocol and to ensure the study is conducted according to GCP. It is important that the investigators and other trial site staff are available at these visits.

It will be the clinical monitor's responsibility to inspect the CRF at regular intervals throughout the study, to verify the adherence to the protocol and the completeness, consistency, and accuracy of the data being entered on them. The investigator agrees to cooperate with the clinical monitor to ensure that any problems detected in the course of these monitoring visits are resolved.

19.5.4. Statement of Good Clinical Practices

This trial will be conducted in adherence to the study protocol, Malaysian Guideline for Good Clinical Practice, Good Clinical Practices (GCP) as defined the ICH E6: Guideline for Good Clinical Practice

(ICH E6 GCP) consolidated guidelines and other applicable regulatory requirements (http://www.fda.gov/cder/guidance/index.htm).

19.5.5. Protocol Adherence

The Investigator must adhere to the protocol as described in this document and agree that deviations to the protocol, with the exception of medical emergencies, must be discussed and approved by the Sponsor prior to seeking approval from the IRB/IEC. The Investigator is responsible for enrolling patients who have met the protocol inclusion and exclusion criteria or must have obtained prior documented approval from the Sponsor prior to enrolment in the study. The IRB/IEC that granted original approval, or the IRB/IEC currently responsible for overseeing the conduct of the study, must be notified of all changes in and deviations from the protocol that may increase risk to the subject, and/or that may adversely affect the rights of the subject or validity of the investigation. The Investigator must send a copy of the approval letter from the IRB/IEC to the Sponsor and retain the original in the site study regulatory file.

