⁹ Samples obtained at screening will be tested retrospectively for NS5A Resistance testing for all patients and for NS5B Resistance testing for treatment failures . For virological failures, NS5A and NS5B Resistance testing will be performed at first point after failure when viral load is sufficient to get a positive result (test can be performed retrospectively on stored samples if needed, see note 10)

¹⁰Tests to be performed retrospectively on stored samples if needed: HCV genotyping, HCV sequencing, HCV resistance testing RAV, sparse drug levels on therapy and IL28B gene. IL28B will be tested systematically and at baseline only on stored samples.

¹¹ In stage 1 only, intensive PK (Predose, 1, 2, 3, 4, 6, 8, 24 hours post dose) in 25 mono-infected patients in selected sites

¹² Sparse PK sampling: a) at W4: 2 samples (Predose, 2-4 hours post dose); b) W8: 1 sample (at any time post dose within 24 hours); c) W12: 2 samples (2 hours apart between 6-26 hours' post-dose) ¹³ Serum creatinine not required for SVR24 only.

¹⁴ A series of long-term follow-up visits will be implemented retrospectively for stage 1 for all patients with virological failure at SVR 12 or SVR 24 and for stage 2 for a representative subset of the cured patients (i.e. achieving SVR 12) and for all patients with virological failure at SVR 12 or SVR 24 (see section 13.5.2).

¹⁵ ECG at SVR4 visit will be performed only on patients showing ECG abnormalities at end of treatment visit
8. Enrolment procedures

All relevant medical and non-medical conditions must be taken into consideration when deciding whether this protocol is suitable for a particular subject. Any questions regarding a subject's eligibility should be discussed with DNDi prior to subject's enrollment. Prior to any clinical procedures and evaluations, written signed informed consent must be obtained.

Screening and enrolment must be completed within a maximum of 30 days.

Procedures completed during Screening visit are described in section 7.

No restrictions will be imposed on the number of subjects in each subgroup (genotype and cirrhotic status) in stage 1. Additional subjects will be enrolled in stage 2 in order to reach ideally 50 subjects per subgroup (30 for GT2) when combining both stages. If recruitment of some subgroups proves very slow, recruitment will be adjusted in other sub-groups to achieve the target of 300 subjects for stage 2 within a reasonable timeframe. This is most likely to apply to genotype 2.

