16.2.1. Analysis Sets

Five analysis sets will be used in this study:

- *All enrolled subjects:* composed of all subjects who signed an informed consent form and were enrolled in the study.
- Safety Analysis Set (SAF): composed of all enrolled subjects who received at least one dose of a study drug. This set will be used for safety analyses.
- *Full Analysis Set (FAS):* composed of all enrolled subjects with no current injection drug use at screening who received at least one dose of a study drug. This set will be used for the primary analysis of SVR endpoints.
- Per Protocol Set (PPS): composed of all subjects in the FAS who did not prematurely discontinue the study, had an adherence to SOF+RDV ≥ 90%, had no missing SVR12 results and had no major protocol deviation during the study. The PPS will only be used for the secondary analysis of SVR endpoints.
- *Pharmacokinetic Analysis Set (PKAS):* composed of all enrolled subjects who participated in the intensive PK analysis or for whom sparse PK data are available.

The reasons for excluding a subject from any of the analysis sets will be described in the clinical study report.

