19.5.6. Protocol deviation

Protocol deviations will be documented in a protocol deviation log and kept at site. If protocol violations are detected, they will be reported promptly to the IEC according to the local regulation. Findings from monitoring visits and deviations reported by study sites will be documented in a central database and reported in the clinical study report.

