19.5.7. Protocol Amendments

The Principal investigator will ensure that the study protocol is strictly adhered to throughout, and that all data are collected and recorded correctly on the CRF. The Principal investigator may contact the sponsor for a protocol waiver for minor deviations from the protocol (e.g. subject unable to attend during visit window).

All protocol modifications must be documented in writing. Any protocol amendment must be approved and signed by the sponsor and the Principal investigator and is to be submitted to the appropriate IEC for information and approval in accordance with local requirements, and to regulatory agencies if required.

Approval by IEC (and Regulatory Authority, if applicable) must be awaited before any changes can be implemented, except for changes necessary to eliminate an immediate hazard to trial subjects, or when the change involves only logistical or administrative aspects of the trial (e.g. change in clinical monitor[s], change of telephone number[s]).

The protocol amendment can be initiated by either sponsor or by any Principal investigator.

The investigator will provide in writing the reasons for the proposed amendment and will discuss with the medical coordinator and sponsor.

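### Section 19.5.5 accepts sponsor approval in place of meeting the entry criteria, with no limit on which criteria and no stated need for prior IRB/IEC approval, and conflicts with section 19.5.7

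*Protocol*

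**What the plan says.** Four places in the protocol bear on whether a patient who fails an entry criterion can be enrolled.

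- **Section 19.5.5, first sentence.** Apart from medical emergencies, deviations "must be discussed and approved by the Sponsor prior to seeking approval from the IRB/IEC".
- **Section 19.5.5, next sentence.** The investigator enrols "patients who have met the protocol inclusion and exclusion criteria or must have obtained prior documented approval from the Sponsor prior to enrolment". Nothing restricts this to particular criteria. The sentence after it adds that the IRB/IEC "must be notified of all changes in and deviations from the protocol that may increase risk to the subject", or that may adversely affect subjects' rights or the validity of the investigation.
- **Section 19.5.7.** "The Principal investigator will ensure that the study protocol is strictly adhered to throughout". The investigator "may contact the sponsor for a protocol waiver for minor deviations from the protocol (e.g. subject unable to attend during visit window").
- **Section 8.** "Any questions regarding a subject's eligibility should be discussed with DNDi prior to subject's enrollment". This provides for discussion and grants no power to waive.

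Reporting is covered in two further places. Section 19.5.6 says: "If protocol violations are detected, they will be reported promptly to the IEC according to the local regulation". It also sends deviations to a central database and the clinical study report. Section 21.2 requires deviations on entry criteria in Malaysia to be reported periodically to the Drug Control Authority.

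On analysis, section 16.2.1 puts into the Full Analysis Set every enrolled, dosed subject without current injection drug use at screening, and uses that set for the primary SVR analysis. The Per Protocol Set, used only for a secondary analysis, keeps subjects who, among other conditions, "had no missing SVR12 results and had no major protocol deviation during the study".

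**The concern.** A clause that accepts sponsor approval as a substitute for eligibility is an eligibility waiver. As worded it reaches the exclusions in section 5.3 that protect patients, such as baseline QTcF, decompensated cirrhosis, hepatocellular carcinoma and HBsAg, as well as prior NS5A inhibitor therapy, which bears on efficacy. A site asking whether the sponsor may approve a patient who fails one of these gets a yes from 19.5.5 and, for anything not minor, no support from 19.5.7.

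Two things are at stake. One is subject protection, because the enrolment sentence does not place ethics review ahead of entry. The other is what the result means. The trial is open label, has no comparator arm, and judges one SVR12 rate against a performance goal of 85%. With no randomised control group, the entry criteria are a main part of what defines the rate. Stage 2 also enrols after the Stage 1 results have been reviewed, so a discretionary entry route would be used by a sponsor that knows those results.

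**Working it through.** **1. The texts side by side**

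| Question | 19.5.5, enrolment sentence | 19.5.5, sentences around it | 19.5.7 | Section 8 |
|---|---|---|---|---|
| Can the sponsor approve entry of a patient who fails a criterion? | Yes, as an alternative to meeting the criteria | Sponsor approves deviations as a first step | Waivers described only for minor deviations | Discussion only |
| Which criteria? | No limit | No limit | Example is a visit window, not an entry criterion | Not applicable |
| Is IRB/IEC approval needed before enrolment? | Not stated | Approval is sought after the sponsor's; notification required, timing not stated | Approval awaited for protocol changes, with exceptions | Not stated |

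The first row is a conflict between 19.5.5 and 19.5.7. The third row is an ambiguity within 19.5.5: the deviation sentence points to ethics approval, while the enrolment sentence names only the sponsor.

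**2. Where a waived patient is counted**

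The Full Analysis Set asks for enrolment, at least one dose and no current injection drug use at screening. A patient waived on any other criterion meets these conditions after one tablet. Whether the Per Protocol Set removes the patient depends on whether a sponsor-approved entry is classed as a major deviation, and section 16.2.1 does not settle that.

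**3. The plan's own figures, for context**

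Section 16.1.1 states over 86% power for 85% against 91% with N = 300, using a two-sided exact binomial test at 0.05. The smallest r with P(X ≥ r | 300, 0.85) ≤ 0.025 is 268, with an upper-tail error of 0.018. Power is P(X ≥ 268 | 300, 0.91) = 0.865, so the stated figure reproduces. In Figure 3, 88% of 600 is 528 responders, with a Clopper-Pearson interval of 85.1% to 90.5%, which also reproduces.

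**4. How far waived patients could move the result**

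The protocol gives no number of waivers, so the shares below are assumptions. Take about 88% SVR12 in eligible patients, the protocol's own threshold for a lower bound above 85%. Let k of the 600 be waived and x be the responders among the 600 − k eligible patients. The lower bound is the 2.5% quantile of Beta(x, n − x + 1).

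| Waived (assumed) | Eligible only | All waived fail | All waived reach SVR12 |
|---|---|---|---|
| 1%, k = 6 | 523/594: 85.2% | 523/600: 84.2% | 529/600: 85.3% |
| 2%, k = 12 | 517/588: 85.0% | 517/600: 83.1% | 529/600: 85.3% |
| 5%, k = 30 | 502/570: 85.1% | 502/600: 80.5% | 532/600: 85.9% |

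The bound can move either way, depending on who is waived. Away from the threshold a small number of waivers does not matter. With about 90% response in 594 eligible patients (535 responders) and six waived patients all failing, 535/600 has a lower bound of 86.4%. With about 95% (564 responders), 564/600 gives 91.8%.

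**The case against.** The strongest reply is that the enrolment sentence should not be read alone. The sentence before it has sponsor approval precede an approach to the IRB/IEC. The one after it requires notification of deviations that raise risk or affect validity, and the section ends by requiring the IRB/IEC approval letter to be filed. Sections 19.5.6 and 21.2 add ethics committee and regulator reporting. A reader might infer from the enrolment sentence that patients can enter on the sponsor's word alone and without ethics review. The protocol does not support that: ethics review is mentioned and reporting is required. What remains is narrower. The text does not say that ethics approval must precede enrolment, and reporting a detected violation or notifying a deviation without a stated time limit can follow the first dose.

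It can also be said that 19.5.7 is permissive and never says waivers are given only for minor deviations, and that its rule about awaiting ethics approval concerns protocol changes, not single patients. Both are correct. The conflict rests on strict adherence and on the described scope of waivers, and that is enough for the two sections to need reconciling.

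Three further inferences do not hold:

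- **The Full Analysis Set is faulty.** Keeping dosed ineligible patients in such a set is usual practice. The weakness is discretionary admission.
- **Stage 2 injection drug users could reach the primary set through a waiver.** Current injection drug use at screening already excludes a subject from it.
- **The Per Protocol Set would retain waived patients.** The protocol does not say so, and what counts as major is commonly left to the statistical analysis plan.

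Finally, the fact that one patient can decide the outcome (527/600 gives 84.95%, 528/600 gives 85.13%) says nothing about waivers. Any exact threshold behaves that way.

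**Conclusion.** The point holds as a conflict within the protocol. Section 19.5.5 offers sponsor approval in place of eligibility, for any criterion and without requiring prior IRB/IEC approval. That cannot be squared with 19.5.7, and it fits poorly with the first sentence of 19.5.5. It is worth correcting because it governs who can be enrolled, including patients the safety exclusions are meant to keep out, and because the population gives the single SVR12 rate its meaning.

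The size and direction of any effect on SVR12 are unknown. The table above rests on assumed waiver shares of 1% to 5% and a response at the protocol's own threshold. It shows that the conclusion could change only near that threshold, and that waived patients who fail would count against the regimen. It is not evidence that any waiver was given or that the result favours the sponsor. No sample-size or power figure is challenged.

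**What to change.** 1. In 19.5.5, delete the second limb of the enrolment sentence, from 'or' to the end of the reference to sponsor approval, and state that inclusion and exclusion criteria are not waived.
2. In section 8, add that discussing an eligibility question with the sponsor serves to clarify a criterion and does not replace meeting it.
3. In 19.5.7, limit waivers to visit logistics, in line with the example already given.
4. Optionally, in 16.2.1 or the statistical analysis plan, state that any breach of an entry criterion, sponsor-approved or not, is a major deviation for the Per Protocol Set. The Full Analysis Set needs no change.

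The cost is one deleted clause, two or three added sentences and a few more screen failures. Deviations already go to a central database and the clinical study report, so no new data collection is needed.
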